5.5 Criteria for Removal from Study

Patients treated in group 1 (Nivolumab alone) are allowed to cross-over to group 2 at the time of documented disease progression. A repeat biopsy is mandatory to confirm progressive disease. Patients who cross-over from group 1 to group 2 may continue treatment for an additional 2 years (counting from the start of treatment on group 2) as long as he or she does not meet other criteria for removal from the study.

Patients will be removed from study when any of the applicable criteria occur: completion of follow-up as described in Section 5.4 above, patient withdrawal, or

inability to follow study protocol as listed in Section 5.3. The reason for study removal and the date the patient was removed must be documented in the Case Report Form.

5.6 Criteria to Resume Treatment Following a Drug-Related Adverse Event

Some patients may continue to benefit from treatment, maintaining or improving responses after developing a drug-related adverse event that requires temporary discontinuation of the study drugs. These may include patient who require treatment with steroids.

Patients who develop drug-related adverse events may resume therapy only if he or she meets the dose modification criteria as described in the tables in Section 6.

If the criteria to resume treatment are met, the patient should restart treatment no sooner than the next scheduled time point per protocol. However, if the treatment is delayed past the next scheduled time point per protocol the treatment should resume at the earliest convenient point that is within the six week delay period.

For patients who develop immune-related adverse events, including those who require treatment with high dose steroids treatment may be resumed if all the following are met:

- Must resolve to baseline within 6 weeks of treatment
- Must be off steroids for at least 2 weeks with no recurrence or new events New immune related events or exacerbation of existing events during steroid treatment or taper suggest the presence of ongoing immune activation and should require permanent discontinuation of nivolumab.
- Must have had no recurrence of symptoms or new symptoms during steroid taper.

5.7 Treatment of Study Drug Related Infusion Reactions

Since nivolumab and CDX-1127 (varlilumab) contain only human immunoglobulin protein sequences, they are unlikely to be immunogenic and induce infusion or hypersensitivity reactions. However, if such a reaction were to occur, it might manifest with fever, chills, rigors, headache, rash, urticaria, angioedema, pruritis, arthralgias, hypo- or hypertension, bronchospasm, or other symptoms.

All Grade 3 or 4 infusion reactions should be reported as an SAE if criteria are met. Infusion reactions should be graded according to NCI CTCAE version 5.0 guidelines.

Treatment recommendations are provided below and may be modified based on local treatment standards and guidelines as medically appropriate:

Remain at bedside and monitor subject until recovery from symptoms.

For Grade 1 symptoms (Mild transient reaction; infusion interruption not indicated; intervention not indicated):

Infusion rate may be slowed or interrupted and restarted at 50% of the original infusion rate when symptoms resolve; if no further complications ensue after 30 minutes, the rate may be increased to 100% of the original infusion rate. Monitor patient closely.

The following prophylactic premedications are recommended for future infusions: diphenhydramine 50 mg (or equivalent) and/or paracetamol 325 to 1000 mg (acetaminophen) at least 30 minutes before additional administrations of study drugs, slowing infusion rate as above.

If the grade 1 event occurs during the infusion of the first drug in patients randomized to the combination therapy arm (group 2), the second drug may still be given as long as the patient is closely monitored and there is no evidence of increase in severity of reaction (beyond grade 1).

For Grade 2 symptoms (Therapy or infusion interruption indicated but responds promptly to symptomatic treatment [e.g., antihistamines, NSAIDS, narcotics, IV fluids]; prophylactic medications indicated for ≤24 hrs):

Stop the study drug infusion, begin an IV infusion of normal saline, and treat the subject with diphenhydramine 50 mg IV (or equivalent) and/or paracetamol 325 to 1000 mg (acetaminophen); remain at bedside and monitor patient until resolution of symptoms. Corticosteroid or bronchodilator therapy may also be administered as appropriate. If the infusion is interrupted, then restart the infusion at 50% of the original infusion rate when symptoms resolve; if no further complications ensue after 30 minutes, the rate may be increased to 100% of the original infusion rate. Monitor patient closely. If symptoms recur, re administer diphenhydramine 50 mg IV, and remain at bedside and monitor the patient until resolution of symptoms. No further study drug will be administered in the setting of a recurrent infusion reaction and the amount of study drug infused must be recorded on the electronic case report form (eCRF).

Close observation for resolution of symptoms and supportive care may need to be continued 24-48 hours. If the event (i.e. recurrent infusion reaction) occurs during the infusion of the first drug in patients randomized to the combination therapy arm (group 2), the second drug will also be held for that day but may be administered the following day as long as infusion-related symptoms have resolved. Given the degree of clinical experience with nivolumab and its known low likelihood of infusion reaction we recommend that it be administered first for those patients in the combination therapy arm (Group 2).

The following prophylactic premedications are recommended for future infusions: diphenhydramine 50 mg (or equivalent) and (acetaminophen) (or paracetamol) 325 to

1000 mg should be administered at least 30 minutes before additional nivolumab administrations. If necessary, corticosteroids (recommended dose: up to 25 mg of IV hydrocortisone or equivalent) may be used.

For Grade 3 or Grade 4 symptoms:

- **Grade 3 symptoms**: Prolonged (e.g., not rapidly responsive to symptomatic medication and/or brief interruption of infusion); recurrence of symptoms following initial improvement; hospitalization indicated for other clinical sequelae
- Grade 4 symptoms: Life-threatening consequences; urgent intervention indicated

Immediately discontinue infusion of the study drug. Begin an IV infusion of normal saline, and bronchodilators, epinephrine 0.2 to 1 mg of a 1:1,000 solution for subcutaneous administration or 0.1 to 0.25 mg of a 1:10,000 solution injected slowly for IV administration, and/or diphenhydramine 50 mg IV with methylprednisolone 100 mg IV (or equivalent), as needed. Patient should be monitored until the investigator is comfortable that the symptoms will not recur.

Investigators should follow their institutional guidelines for the treatment of anaphylaxis. Remain at bedside and monitor patient until recovery from symptoms.

For Grade 4 infusion reactions, study drug(s) will be permanently discontinued.

Patients with Grade 3 infusion reactions who have not been pre-medicated may continue study treatment with appropriate pre-medication, at the discretion of the investigator. Recommended prophylactic pre-medications for all subsequent infusions as described in management of Grade 2 infusion reactions. Study drug(s) should be permanently discontinued for recurrence of Grade 3 infusion reaction for patients who have received pre-medications.

In the case of late-occurring hypersensitivity symptoms (*e.g.*, appearance of a localized or generalized pruritis within 1 week after treatment), symptomatic treatment may be given (*e.g.*, oral antihistamine, or corticosteroids). Additional treatment prior to next dose as per guidelines above.

Please note that late occurring events including isolated fever and fatigue may represent the presentation of systemic inflammation. Please evaluate accordingly.

6. DOSING DELAYS/DOSE MODIFICATIONS

6.1 Dose Modifications for Group 1 (Nivolumab alone) and Group 2 (Nivolumab and CDX-1127 (Varlilumab)

Below are DOSE MODIFICATION tables applicable to all patients participating in this study for the following adverse events. This applies to all patients whether they have been assigned to Group 1 (nivolumab alone) or Group 2 (nivolumab and CDX-1127 (variiumab)

Patients who develop adverse events while being treated with combinatory therapy CDX-1127 (varlilumab and nivolumab - Group 2 patients) must have both drugs held or discontinued according to the guidance provided in the tables below. Treatment with single-agent will not be permitted at any time for patients who are randomized to Group 2 and develop adverse events.

Please use as written and contact the drug monitor for any proposed changes. Note that if a patient experiences several adverse events and there are conflicting recommendations, the investigator should use the recommended treatment modification for the most serious event that has a higher level of modification, i.e. going off study treatment versus holding drug.

A patient who requires treatment to be held within the first 4 months on the study will continue to receive nivolumab at the dosage of 240 mg every 2 weeks if he meets criteria to resume treatment before the 4 months' timepoint. For this patient, the change in dosage and frequency of nivolumab (from 240 mg every 2 weeks to 480 mg every 4 weeks) should occur at the 4-month mark regardless of the number of nivolumab infusions received prior to holding treatment. However, if the same patient only meets criteria to resume treatment after the 4-month mark he or she will resume treatment with nivolumab 480 mg every 4 weeks regardless of the total number of nivolumab infusions received up to that point.

In several places there are differences between the protocol specific guidelines in Section 6.1 and the toxicity management algorithms in Appendix D. In these instances, the protocol specific guidelines should be followed. These treatment guidelines and management algorithms should be followed unless there are specific clinical circumstances for which the treating physician decides an alternative treatment approach is clinically appropriate. Consultation with the study PI or drug monitor is recommended.

Generally we strongly encourage early evaluation while withholding drug, and appropriate treatment as indicated in the management tables and event specific guidelines.

Dose hold = All study drugs must be held. Day 1 of the next cycle is given when the patient meets the protocol criteria to restart drugs. The current cycle will include all days until the patient resumes treatment and may be longer than 28 days.

ALL OTHER EVENTS	Management/Next Dose	
≤ Grade 1	No change in dose	

ALL OTHER EVENTS	Management/Next Dose
Grade 2	Hold until \leq Grade 1 OR baseline (exceptions as noted below)
Grade 3	Off protocol therapy (exceptions as noted below)
Grade 4	Off protocol therapy
Recommended management: As clinically indicated	

• Any grade 2 drug-related uveitis or eye pain or blurred vision that does not respond to topical therapy and does not improve to Grade 1 severity within the retreatment period OR requires systemic treatment should go off protocol treatment

- Any adverse event, laboratory abnormality, or intercurrent illness which, in the judgment of the investigator, presents a substantial clinical risk to the subject with continued study drug dosing should go off protocol treatment.
- Any grade 3 or 4 drug-related laboratory abnormality or electrolyte abnormality, that can be managed independently from underlying organ pathology with electrolyte replacement, hormone replacement, insulin or that does not require treatment **does not** require discontinuation.
- Lymphopenia is an expected event for both study drugs. Asymptomatic lymphopenia does not constitute reason to hold or discontinue the study drugs, regardless of the grade

Skin Rash and Oral Lesions	Management/Next Dose
≤ Grade 1	No change in dose *
Grade 2	Hold* until $1 \le$ Grade resolved. Resume at same dose level.
Grade 3	Hold* until \leq Grade 1. Resume at same level at investigator discretion
Grade 4	Off protocol therapy
*Patients with purpuric or bullous lesions must be evaluated for vasculitis, Steven-Johnson syndrome, TEN, and autoimmune bullous disease including oral lesions of bullous pemphigus/pemphigoid. Pruritus may occur with or without skin rash and should be treated symptomatically if there is no associated liver or GI toxicity. Note skin rash typically occurs early and may be followed by additional events particularly during steroids tapering.	
Recommended management: AE management guidelines	

Liver Function	
AST, ALT,	Management/Next Dose
Bilirubin	

Liver Function AST, ALT, Bilirubin	Management/Next Dose
≤Grade 1	Hold until UNL or baseline. Resume at same dose level.
Grade 2	Hold until UNL or baseline. Resume at same dose level.
Grade 3	Off protocol therapy
Grade 4	Off protocol therapy
Continued treatment of active immune mediated hepatitis may exacerbate ongoing inflammation.	
Holding drug to evaluate LFT changes and early treatment are recommended.	
LFT changes may occur during steroid tapers from other events and may occur together with other GI	

events including cholecystitis/pancreatitis.

Recommended management: see Hepatic AE management algorithm

Diarrhea/ Colitis	Management/Next Dose
≤ Grade 1	Hold until baseline. No change in dose
Grade 2	Hold until baseline. No change in dose
Grade 3	Off protocol therapy.
Grade 4	Off protocol therapy
See GI AE Algorithm for	or management of symptomatic colitis.
Patients with grade 2 symptoms but normal colonoscony and bionsies may be retreated after resolution	

Patients with grade 2 symptoms but normal colonoscopy and biopsies may be retreated after resolution. Patients who require steroids should be taken off study treatment.

Please evaluate pituitary function prior to starting steroids if possible without compromising acute care. Evaluation for all patients for additional causes includes *C. diff*, acute and self-limited infectious and foodborne illness, ischemic bowel, diverticulitis, and IBD.

Recommended management: see GI AE management Algorithm

Pancreatitis Amylase/Lipase	Management/Next Dose
≤ Grade 1	Hold dose until baseline. Resume at same dose level if asymptomatic
Grade 2	Hold until baseline. Resume at same dose level if asymptomatic
Grade 3	Hold until baseline. Resume at same dose level if asymptomatic. Patients who develop symptomatic pancreatitis or DM should be taken off treatment
Grade 4	Hold until baseline. Resume at same dose level if asymptomatic. Patients who develop symptomatic pancreatitis or DM should be taken off treatment
Patients may develop symptomatic and radiologic evidence of pancreatitis as well as DM and	
DKA. Lipase elevation may occur during the period of steroid withdrawal and with other immune mediated events or associated with colitis, hepatitis, and patients who have	
asymptomatic lipase elevation typically have self-limited course and may be retreated.	
For treatment management of symptomatic pancreatitis please follow the Hepatic Adverse	
Event Management Algorithm	

Pneumonitis Management/Next Dose

Pneumonitis	Management/Next Dose
≤ Grade 1	Hold dose pending evaluation and resolution to baseline including
	baseline pO2. Resume no change in dose after pulmonary and/or ID
	consultation excludes lymphocytic pneumonitis.
Grade 2	Hold dose pending evaluation. Off protocol therapy if steroids are
	required.
Grade 3	Hold dose pending evaluation. Off protocol therapy if steroids are
	required
Grade 4	Off protocol therapy
	matory pneumonitis is often a diagnosis of exclusion for patients who do not
respond to antibiotics	and have no causal organism identified including influenza. Most patients with

respond to antibiotics and have no causal organism identified including influenza. Most patients with respiratory failure or hypoxia will be treated with steroids. Bronchoscopy may be required and analysis of lavage fluid for lymphocytic predominance may be helpful. Patients with new lung nodules should be evaluated for sarcoid like granuloma. Please consider recommending seasonal influenza killed vaccine for all patients.

Recommended management: See Pulmonary Adverse Event Management Algorithm

Other GI (not Nausea and Vomiting)	Management/Next Dose
≤Grade 1	No change in dose.
Grade 2	Hold pending evaluation for gastritis duodenitis and other immune adverse events or other causes. Resume at same dose level after resolution to \leq Grade 1.
Grade 3	Hold pending evaluation until \leq Grade 1. Resume at same dose level. If symptoms do not resolve within 7 days with symptomatic treatment patients should go off protocol therapy
Grade 4	Off protocol therapy
Patients with grade 2 or events.	3 N-V should be evaluated for upper GI inflammation and other immune related

Fatigue	Management/Next Dose	
≤Grade 1	No change in dose.	
Grade 2	No change in dose	
Grade 3	Hold until \leq Grade 2. Resume at same dose level	
Fatigue is the most common adverse event associated with immune checkpoint therapy. Grade		
2 or greater fatigue should be evaluated for associated or underlying organ involvement		
including pituitary, thyroid, and hepatic, or muscle (CPK) inflammation		

Neurologic events	Management/Next Dose
≤ Grade 1	Hold dose pending evaluation and observation. Resume with no change in dose when resolved to baseline.
Grade 2	Hold dose pending evaluation and observation. Hold until \leq Grade 1. Off protocol therapy if treatment with steroids is required. Resume at

Neurologic events	Management/Next Dose	
	same dose level for peripheral isolated n. VII (Bell's palsy)^	
Grade 3	Off protocol therapy	
Grade 4	Off protocol therapy	
Patients with any CNS events including aseptic meningitis, encephalitis, symptomatic		
hypophysitis, or myopathy, peripheral demyelinating neuropathy, cranial neuropathy (other		
than peripheral n. VII), GB syndrome and myasthenia gravis should be off study.		
Recommended management: See Neurologic Adverse Event Management Algorithm		

Endocrine Hypophysitis Adrenal Insufficiency	Management/Next Dose			
≤ Grade 1	Asymptomatic TSH elevation * Hold pending evaluation, endocrine			
	consult			
	Hold until patients are on a stable replacement hormone regimen. If			
Grade 2	treated with steroids patients must be stable off steroids for two weeks.			
	Resume at same dose level.			
Grade 3	Off study treatment.			
Grade 4	Off protocol therapy			
Note all patients with syn	Note all patients with symptomatic pituitary enlargement, exclusive of hormone deficiency, but			
including severe headach	including severe headache or enlarged pituitary on MRI should be considered grade 3 events. Isolated			
thyroid or testosterone deficiency may be treated as grade 2 if there are no other associated deficiencies				
and adrenal function is monitored.				
Please evaluate pituitary function before beginning steroid therapy or replacement therapy of any kind.				
*Note patients with thyroiditis may be retreated on replacement therapy. Patients must be evaluated to				
rule out pituitary disease prior to initiating thyroid replacement.				
Recommended manage	Recommended management: See Endocrine Management Algorithm			

Creatinine Increased	Management/Next Dose	
≤Grade 1	No change in dose. Monitor toxicity weekly until returned to baseline.	
Grade 2	Hold until \leq Grade 1. Resume at same dose level.	
Grade 3	Hold until \leq Grade 1. Resume at same dose level.	
Grade 4	Off treatment	
Recommended management: See Renal Management Algorithm		

Infusion Reaction	Management/Next Dose		
< Grade 1	Infusion may be slowed or interrupted until symptoms resolve. See		
	Section 5.7 for details on management and subsequent dosing.		
Grade 2	Interrupt until symptoms resolve. See Section 5.7 for details on		

Management/Next Dose		
management and subsequent dosing.		
Immediately discontinue infusion. See Section 5.7 for details on management and subsequent dosing.		
Immediately discontinue infusion. See Section 5.7 for details on management. Permanently discontinue study drug(s).		
-		

Patients with fever should be evaluated as clinically appropriate. Patients may experience isolated fever during infusion reactions or up to several days after infusion. Evaluation over the course of 1-2 weeks should be done for other autoimmune events that may present as fever

Fever	Management/Next Dose		
≤ Grade 1	Evaluate and continue at same dose level		
Grade 2	Hold until \leq Grade 1. Resume at same dose level.		
Grade 3	Hold until \leq Grade 1. Resume at same dose level.		
Grade 4	Off treatment		
Patients with fever should be evaluated as clinically appropriate. Patients may experience			
isolated fever during in	nfusion reactions or up to several days after infusion. Evaluation over the		
course of 1-2 weeks should be done for other autoimmune events that may present as fever			
See section 5. infusion reactions			

Cardiac *	Management/Next Dose for Cardiac Toxicities	
≤ Grade 1	Hold dose pending evaluation and observation.** Evaluate for signs and symptoms of CHF, ischemia, arrhythmia or myositis. Obtain history EKG, CK (for concomitant myositis), CK-MB. Repeat troponin, CK and EKG 2-3 days. If troponin and labs normalize may resume therapy. If labs worsen or symptoms develop then treat as below. Hold pending evaluation	
Grade > 2 with suspected myocarditis	Hold dose.** Admit to hospital. Cardiology consult. Rule out MI and other causes of cardiac disease. Cardiac Monitoring. Cardiac Echo. Consider cardiac MRI and cardiac biopsy. Initiate high dose methylprednisolone. If no improvement within 24 hours, add either infliximab, ATG or tacrolimus. Consult algorithm for more details. Resume therapy if there is a return to baseline and myocarditis is excluded or considered unrelated.	
Grade ≥2 with confirmed myocarditis	Off protocol therapy. Admit to CCU (consider transfer to nearest Cardiac Transplant Unit). Treat as above. Consider high dose methylprednisolone Add ATG or tacrolimus if no improvement. Off treatment.	
 * Including CHF, LV systolic dysfunction, Myocarditis, CPK, and troponin **Patients with evidence of myositis without myocarditis may be treated according as "other event" Note: The optimal treatment regimen for immune mediated myocarditis has not been 		

established. Since this toxicity has caused patient deaths, an aggressive approach is recommended.

- Drug will be held for grade 2 cardiac dysfunction pending evaluation
- Drug will be permanently discontinued for grade 3 or 4 cardiac dysfunction and grade 2 events that do not recover to baseline or that reoccur
- Treatment with steroids as clinically indicated

If treatment is delayed > 6 weeks for an adverse event, the patient must be permanently discontinued from study therapy.

Patients requiring high dose steroid treatment for autoimmune or inflammatory events should go off study treatment except for a short course of tapering steroids for infusion reaction, skin rash or endocrine events.

Patients with grade 3 thyroiditis and skin rash may continue therapy with resolution and stable replacement treatment.

Patients with thyroiditis or hypopituitarism who are stable as above may be restarted with replacement hormones including thyroid hormone and physiologic doses of corticosteroids. Please note that grading and for hypophysitis with symptoms of headache, visual or neurologic changes or radiologic evidence of pituitary enlargement and other CNS events such as aseptic meningitis or encephalitis should be considered grade 3 events.

Any patients who require additional immune suppressive treatment beyond steroids should go off study treatment

Patients requiring > two dose delays for the same event should go off protocol therapy.

Prior to starting corticosteroids or hormone replacement for any reason, appropriate endocrine testing including cortisol, ACTH, TSH and T4 must be obtained to document baseline.

Please note that in some cases the treatment algorithms recommend steroids if symptoms do not resolve in 7 days. However, this recommendation is not meant to delay steroid treatment at any time it is clinically indicated.

Patients may be dose-delayed for evaluation and restarted depending on results. Any patient started on corticosteroids initially who is determined to not require steroid treatment for an autoimmune adverse event may resume therapy after a 2 week observation period without further symptoms at the discretion of the PI or investigator.

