5.2 General Concomitant Medication and Supportive Care Guidelines

Because there is a potential for interaction of CDX-1127 (varlilumab) and nivolumab with other concomitantly administered drugs, the case report form must capture the concurrent use of all other drugs, over-the-counter medications, or alternative therapies. Appendix B, the Patient Wallet Card, will be given to patients to identify the study physician and provide a contact telephone number.

5.3 **Duration of Therapy**

In the absence of treatment delays due to adverse event(s), treatment may continue for up to a maximum of 2 years or until one of the following criteria applies:

- Disease progression (except patients on group 1 who wish to cross-over to group 2),
- Intercurrent illness that prevents further administration of treatment,
- Adverse event(s) which require(s) permanently going off study treatment (see also section 6 and specific algorithms in Appendix E)
- Any dosing interruption lasting > 6 weeks, with the following exceptions: Dosing

interruptions > 6 weeks that occur for non-drug-related reasons may be allowed if approved by the Investigator. Prior to re-initiating treatment in a subject with a dosing interruption lasting > 6 weeks, the Principal Investigator must be consulted.

- Patient decides to withdraw from the study
- General or specific changes in the patient's condition render the patient unacceptable for further treatment in the judgment of the investigator
- Clinical deterioration as defined by acute or progressive decline in performance status, progressive debility or progressive increase in tumor-associated symptoms that negatively impact the patient's quality of life as judged by the treating physician.
- Patient non-compliance
- Pregnancy
 - All women of child bearing potential should be instructed to contact the investigator immediately if they suspect they might be pregnant (e.g., missed or late menstrual period) at any time during study participation.
 - The investigator must immediately notify CTEP in the event of a confirmed pregnancy in a patient participating in the study.
- Termination of the study by sponsor
- The drug manufacturer can no longer provide the study agent

The reason(s) for protocol therapy discontinuation must be documented in the Case Report Form (CRF).

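### Two restart instructions contradict the stop rules at the end of Section 6.1, and the protocol does not say which governs

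*Combined protocol and SAP*

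**What the plan says.** **Restart texts.**

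- Section 6.1, Cardiac table, Grade 2 or higher with suspected myocarditis. The row instructs "Initiate high dose methylprednisolone. If no improvement within 24 hours, add either infliximab, ATG or tacrolimus". It closes with "Resume therapy if there is a return to baseline and myocarditis is excluded or considered unrelated". It sets no condition on which immunosuppressants were used.
- Section 5.6, on immune-related events: "including those who require treatment with high dose steroids treatment may be resumed if all the following are met". The conditions are resolution to baseline within 6 weeks, at least 2 weeks off steroids, and no recurrent or new symptoms during the taper. The same section says that a patient "may resume therapy only if he or she meets the dose modification criteria as described in the tables in Section 6".

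**Stop texts, both in the free text after the Cardiac table in Section 6.1.**

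- High-dose steroids: "Patients requiring high dose steroid treatment for autoimmune or inflammatory events should go off study treatment except for a short course of tapering steroids". The exception is confined to infusion reaction, skin rash and endocrine events.
- Further immunosuppression: "Any patients who require additional immune suppressive treatment beyond steroids should go off study treatment". The sentence carries no exception.

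**Carve-out.** The last paragraph of Section 6.1 lets a patient who was started on corticosteroids, and then found not to need them for an autoimmune event, resume after 2 weeks of observation. It speaks of corticosteroids only.

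**The concern.** Each restart text permits what a stop text rules out. In the cardiac row, the table itself orders the drug that triggers the stop rule. In Section 5.6, restart after high-dose steroids is open to any immune-related event, while the closing text of Section 6.1 opens it to three kinds.

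A site working from the row or from Section 5.6 may restart. A site working from the closing text would stop. Section 6.1 does not let patients randomized to Group 2 continue on one drug after an adverse event, so for them the choice is re-exposure to both drugs or loss of both. The Cardiac table itself notes that immune-mediated myocarditis has caused deaths. What is at stake is patient safety and consistent conduct across sites.

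**Working it through.** The plan gives no figure to reproduce. The check applies every restart text, stop rule and carve-out to each case, and then looks for a text that settles any disagreement.

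**Step 1. Cases**

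| Case | Restart text | Stop text | Result |
|---|---|---|---|
| Suspected myocarditis, Grade 2, given infliximab, ATG or tacrolimus; back to baseline; myocarditis excluded or judged unrelated | Cardiac row: resume | Beyond-steroids rule: off treatment; the carve-out covers corticosteroids only | Conflict |
| Grade 2 myositis without myocarditis, needing high-dose steroids | Cardiac footnote sends it to the other-events table (hold, then resume); Section 5.6 permits restart | High-dose-steroid rule: off treatment; not among the exceptions | Conflict |
| Grade 2 liver event needing high-dose steroids | Liver table (hold, then resume); Section 5.6 | Same rule | Conflict |
| Grade 2 or 3 creatinine increase from an immune-related event needing high-dose steroids | Creatinine table (hold, then resume); Section 5.6 | Same rule | Conflict |
| Suspected myocarditis, Grade 2, steroids only, found not to be needed for an autoimmune event | Cardiac row and carve-out: may resume | None applies | No conflict |
| Colitis, or Grade 2 or 3 pneumonitis, needing steroids | Own table already says off treatment, so the Section 5.6 test fails | Agrees | No conflict |
| Grade 3 or 4 myositis needing high-dose steroids | Other-events table: off protocol therapy | Agrees | No conflict |
| Short steroid taper for rash, infusion reaction or endocrine event | Section 5.6 | Listed exceptions | No conflict |

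The cardiac conflict matters mainly at Grade 2. A separate bullet after the Cardiac table permanently discontinues drug for Grade 3 or 4 cardiac dysfunction.

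**Step 2. Is there a text that settles it?**

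- The introduction to Section 6.1 ranks its guidelines above the Appendix D algorithms. It does not rank Section 6.1 against Section 5.6, or a table row against the free text.
- Its rule to follow the higher level of modification is for a patient with several adverse events. Here two rules meet on one event.
- Section 5.6 makes restart conditional on the tables in Section 6. The stop sentences stand after the tables.
- Section 5.3 ends treatment for "Adverse event(s) which require(s) permanently going off study treatment (see also section 6 and specific algorithms in Appendix E", a general pointer to Section 6.
- The Grade 2 line of the other-events table refers to exceptions noted below it, without saying which.
- The cardiac row refers the reader to an algorithm, but the title of Appendix D lists no cardiac one.

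None of these decides the conflicting cases.

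**Step 3. Size**

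The nivolumab adverse event list (2069 patients) puts myocarditis, myositis, immune-mediated hepatitis and immune-mediated nephritis in its under-3% column. As a ceiling per term, that gives fewer than 0.03 × 96 = 2.88 of the 96 evaluable patients, or 0.03 × 48 = 1.44 per group. Liver enzyme and creatinine rises stand in the up-to-20% column, giving at most 0.20 × 96 = 19.2 patients per term. These are column limits for the whole term. They say nothing about how many patients would need high-dose steroids or a second agent, recover in time and be candidates for restart. The documents give no rate for that subset, nor for suspected myocarditis later excluded.

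**The case against.** The best reply is that the texts can be read together. Section 5.6 is permissive: it sets a recovery test and orders no one to restart. The closing text of Section 6.1 then names the events eligible after high-dose steroids, and the Section 5.6 clause still has work to do for those three. The pointers in Section 5.3 and in the other-events table favour this stricter reading. Section 6.1 also lets the treating physician depart from the guidelines in specific clinical circumstances, and recommends consulting the study PI or drug monitor.

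Much of this stands. A cautious site would probably stop. But Section 5.6 names the tables only and does not confine its high-dose-steroid clause to three events. The colitis and pneumonitis tables state a steroid stop, while the liver and creatinine tables and the myositis route do not. Discretion with consultation does not tell a site which written rule is the default.

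On the cardiac row, one can argue that a patient in whom myocarditis was excluded never *required* the second agent. Against that, the row orders it after 24 hours without improvement, and restart is also allowed when myocarditis is judged unrelated rather than excluded. The path is narrow, though: Grade 2, no early improvement, a second agent given, full recovery, and a delay of no more than 6 weeks.

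**Conclusion.** The contradiction is real in both places, and is clearest in the cardiac row. It is a minor safety-conduct correction. Qualifying patients should be few because several conditions must all be met, but that is a judgement and cannot be sized from the documents. Sample size, alpha and the primary analysis are unaffected.

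Four stronger inferences are not supported:

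- **That the Section 5.6 problem is peculiar to myositis.** A reader might infer this because the Cardiac footnote routes it explicitly ("Patients with evidence of myositis without myocarditis may be treated according as" an other event). The conflict reaches any held-and-resumed immune event whose table states no steroid stop.
- **That every patient given steroids for suspected myocarditis is caught.** The carve-out covers those whose steroids proved unnecessary for an autoimmune event.
- **That the closing text makes stopping mandatory.** Both sentences say *should*. The same text uses *must* for treatment delays over 6 weeks, and Section 6.1 allows case-by-case departure.
- **That the number of affected patients can be estimated.** The column limits above are ceilings for whole terms. Any rate for the subset would be a bare assumption.

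**What to change.** Apply the protocol's own stop rules to both restart texts.

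1. In Section 5.6, replace the reference to the tables in Section 6 with *all of Section 6.1, including the text after the tables*. State that restart after high-dose steroids is limited to the exceptions listed there (a short taper for infusion reaction, skin rash or endocrine events) and to the carve-out in the last paragraph of Section 6.1.
2. In the suspected-myocarditis row, add to the restart sentence: *and no immune suppression beyond steroids was given; the steroid rules below also apply*.

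No separate edit to the myositis footnote is needed once the first change is made.

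The second edit has one consequence that the sponsor should confirm. A patient treated with steroids alone for an inflammatory myocarditis judged unrelated to study drug would then fall under the high-dose-steroid rule, although the row as written allows restart.

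The cost is two wording changes in an amendment, with no change to design or analysis. The downside is that a few patients who might have restarted lose study treatment.
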